7 STATISTICAL ANALYSES

7.1 General Methods

Unless otherwise noted, discrete variables will be tabulated by the frequency and proportion of subjects falling into each category, grouped by treatment. Percentages given in these tables will be rounded to the first decimal and, therefore, may not always sum to 100%. Percentages less than 0.1 will be indicated as ‘< 0.1’. Continuous variables will be summarized by treatment group using the mean, standard deviation, median, minimum, and maximum values.

The conventions to be used for imputing missing and partial dates for analyses requiring dates are described in [Section 8](#).

Analyses will be performed for each cohort separately.

7.1.1 *Adverse Events, Serious Adverse Events, Multiple events, Select Adverse Events, Other Events of Special Interest and Immune-Mediated Adverse Events*

Drug-related AEs are those events with relationship to study drug “Related”, as recorded on the CRF. If the relationship to study drug is missing, the AE will be considered as drug-related.

Serious adverse events consist of AEs deemed serious by the Investigator and flagged accordingly in the CRF and clinical database.

Adverse events leading to study drug discontinuation are AEs with action taken regarding study drug(s) = “Drug was discontinued”.

Adverse events leading to dose delay are AEs with action taken regarding study drug(s) = “Drug was delayed”.

Adverse events leading to dose reduction are AEs with action taken regarding study drug(s) = “Dose was reduced”.

Adverse events will be coded using the Medical Dictionary for Regulatory Activities (MedDRA), and the most recent version of the dictionary at the time of the database lock will be used. Adverse event results will be graded for severity using the NCI Common Terminology Criteria for Adverse Events (CTCAE) and the version of the criteria specified in the protocol will be used.

In the AE summary tables, unless otherwise specified, subjects will be counted only once at the Preferred Term (PT), only once at the System Organ Class (SOC), and only once at subject level for the counting of total number of subjects with an AE. The AE tables will be sorted by the SOCs and then PTs. SOC will be ordered by descending frequency overall and then alphabetically. PTs will be ordered within SOC by descending frequency overall and then alphabetically. The sorting

will be done based on the ‘Any Grade’ column of the experimental arm when arms are presented side-by-side.

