7.1.1.2 Other Events of Special Interest

Other events of special interest (OEOSI) consist of a list of preferred terms grouped by specific category. The list of MedDRA preferred terms used to identify OEOSI is revisited quarterly and updated accordingly. The preferred terms used for the selection at the time of the database lock by categories will be provided.

7.1.1.3 *Immune-Mediated Adverse Events*

In order to further characterize AEs of special clinical interest, analysis of immune-mediated AEs (IMAE) will be conducted. IMAEs are specific events (or groups of PTs describing specific events) considered as potential immune-mediated events by investigator that meet the definition summarized below:

- those occurring within 100 days of the last dose,
- regardless of causality,
- treated with immune-modulating medication (of note, endocrine AEs are considered IMAEs regardless of immune-modulating medication use, since endocrine drug reactions are often managed without immune-modulating medication).
- with no clear alternate etiology based on investigator assessment, or with an immune-mediated component

The list of MedDRA preferred terms used to identify IMAEs is revisited quarterly and updated accordingly. The preferred terms used for the selection at the time of the database lock by categories will be provided.

7.1.2 *Laboratory Tests*

Clinical laboratory parameters (hematology, serum chemistry and electrolytes) will be evaluated.

Laboratory tests will be graded using the NCI Common Terminology Criteria, and the most recent version of the criteria at the time of the database lock will be used.

Clinical laboratory data will be analyzed using International System of Units (SI) and repeated using US conventional units.

In the laboratory summary tables, unless otherwise specified, subjects will be counted only once for each lab parameter according to their worst on treatment CTC grade (worst being the highest CTC grade). The laboratory tables and listings will be sorted by laboratory category, laboratory subcategory and laboratory test code sequence number.

7.2 *Study Conduct*

7.2.1 *Accrual*

By subject listing of informed consent (and re-consent if available), randomization date, first dosing date, country, investigational site will be provided.

7.2.2 *Relevant Protocol Deviations*

Not Applicable.

7.3 *Study Population*

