7.6.5 Adverse Events

Adverse events will be summarized by treatment group.

The following analyses will be conducted using the 30 days safety window only:

- Overall summary of any AEs by worst CTC grade (1, 2, 3, 4, 5, not reported, total) presented by SOC/PT.
- Overall summary of any AEs presented by worst CTC grade (any grade, grade 3-4, grade 5) by SOC/PT. This table will be restricted to events with an incidence greater or equal to 5% in any treatment group.
- Overall summary of drug-related AEs by worst CTC grade (1, 2, 3, 4, 5, not reported, total) presented by SOC/PT.

A by-subject AE listing will be provided. A by-subject listing of any AE requiring immune modulating medications will also be provided.

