7.6.6 Select Adverse Events

Analyses will be performed by select AE category.

7.6.6.1 *Incidence of Select AE*

Select AEs will be summarized by treatment group for each category/subcategory.

The following analyses will be conducted using the 30-day safety window only:

- Overall summaries of any select AEs by worst CTC grade (any grade, grade 3-4, grade 5) presented by Category or Subcategory/PT.
- Overall summaries of any drug-related select AEs by worst CTC grade (any grade, grade 3-4, grade 5) presented by Category or Subcategory/PT.

A by-subject select AE listing will be provided.

7.6.6.2 *Time-to Onset of Select AE*

Not Applicable.

7.6.6.3 *Time-to Resolution of Select AE*

Not Applicable.

7.6.7 *Immune-Mediated Adverse Events*

IMAEs will be summarized by treatment group for each immune-mediated category / PT using the 100-day safety window:

- Overall summary of non-endocrine IMAEs by worst CTC grade (any grade, grade 3-4, grade 5) where immune modulating medication was initiated presented by Category / PT.
- Overall summary of endocrine IMAEs by worst CTC grade (any grade, grade 3-4, grade 5) presented by Category / PT.

A by-subject listing of IMAEs will be provided. By-subject listings of time-to resolution for longest IMAEs cluster (any grade and grade 3-5 in separate summaries) will also be provided.

7.6.8 *Other Events of Special Interest*

A by-subject listing of OEOSI will be provided.

7.6.9 *Multiple Events*

Not applicable.

7.6.10 *Laboratory Parameters*

The analysis population for each laboratory test is restricted to treated subjects who underwent that laboratory test. Laboratory tests (in addition to the tests specified below) with CTC criteria collected in the specific studies may also be included in the summaries.

7.6.10.1 *Hematology*

The following will be summarized by treatment group as worst CTC grade on-treatment per subject and as shift table of worst on-treatment CTC grade compared to baseline CTC grade per

subject: hemoglobin (HB), platelets, white blood counts (WBC), absolute neutrophils count (ANC) and lymphocyte count (LYMPH).

The analyses will be conducted using the 30-day safety window.

A by-subject listing of these laboratory parameters will be provided.

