7.6.10.2 Serum Chemistry

The following will be summarized by treatment group as worst CTC grade on-treatment per subject and as shift table of worst on-treatment CTC grade compared to baseline CTC grade per subject: ALT, AST, alkaline phosphatase (ALP), total bilirubin and creatinine.

The analyses will be conducted using the 30-day safety window.

A by-subject listing of these laboratory parameters will be provided.

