7.6.10.3 Electrolytes

The following will be summarized by treatment group as worst CTC grade on-treatment per subject and as shift table of worst on-treatment CTC grade compared to baseline CTC grade per subject: sodium (high and low), potassium (high and low), calcium (high and low), magnesium (high and low), and Glucose Serum (fasting hyperglycemia and hypoglycemia regardless of fasting status).

The analyses will be conducted using the 30-day safety window.

A by-subject listing of these laboratory parameters will be provided.

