7.6.10.4 Additional Analyses

In addition, further analyses on specific laboratory parameters will be performed by treatment group:

Abnormal Hepatic Function Test

The number of subjects with the following laboratory abnormalities from on-treatment evaluations will be summarized by treatment group:

- ALT or AST > 3 x ULN, > 5 x ULN, > 10 x ULN and > 20 x ULN
- Total bilirubin > 2 x ULN
- Concurrent (within 1 day) ALT or AST > 3 x ULN and total bilirubin > 2 x ULN
- Concurrent (within 30 days) ALT or AST > 3 x ULN and total bilirubin > 2 x ULN

The analyses will be conducted using the 30-day safety window.

A by-subject listing of these specific abnormalities will be provided.

Abnormal Thyroid Function Test

The number of subjects with the following laboratory abnormalities from on-treatment evaluations will be summarized by treatment group:

- TSH value > ULN and

- with baseline TSH value \leq ULN
- with at least one FT3/FT4 test value $<$ LLN within 2-week window after the abnormal TSH test
- with all FT3/FT4 test values \geq LLN within 2-week window after the abnormal TSH test
- with FT3/FT4 missing within 2-week window after the abnormal TSH test.

- TSH $<$ LLN and
 - with baseline TSH value \geq LLN
 - with at least one FT3/FT4 test value $>$ ULN within 2-week window after the abnormal TSH test
 - with all FT3/FT4 test values \leq ULN within 2-week window after the abnormal TSH test
 - with FT3/FT4 missing within 2-week window after the abnormal TSH test

The analyses will be conducted using the 30-day safety window.

A by-subject listing of these specific abnormalities will be provided.

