9 CONTENT OF REPORTS

The analyses described in this SAP will be included in the abbreviated Clinical Study Report except where otherwise noted. Additional exploratory analyses may be performed. Refer to the Data Presentation Plan for mock-ups of all tables and listings.

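### Does grading laboratory tests with the newest CTC version at database lock, but adverse events with the protocol's version, undermine the laboratory tables?

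*SAP*

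**What the plan says.** Section 7.1.1 covers adverse events. MedDRA coding follows the version current at database lock, but for CTCAE severity "the version of the criteria specified in the protocol will be used". Section 7.1.2 covers laboratory tests, and there "the most recent version of the criteria at the time of the database lock will be used". Neither section gives a version number or explains why the rules differ.

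The adverse event rule feeds tables such as "Overall summary of any AEs by worst CTC grade (1, 2, 3, 4, 5, not reported, total) presented by SOC/PT" (section 7.6.5). The laboratory rule feeds three groups of tables:

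- hematology (7.6.10.1): "hemoglobin (HB), platelets, white blood counts (WBC), absolute neutrophils count (ANC) and lymphocyte count (LYMPH";
- serum chemistry (7.6.10.2): ALT, AST, alkaline phosphatase, total bilirubin and creatinine;
- electrolytes (7.6.10.3): "sodium (high and low), potassium (high and low), calcium (high and low), magnesium (high and low), and Glucose Serum".

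Each group is presented "as worst CTC grade on-treatment per subject and as shift table of worst on-treatment CTC grade compared to baseline CTC grade". Section 7.6.10.4 adds tables with cut-offs of its own, for example "ALT or AST > 3 x ULN, > 5 x ULN, > 10 x ULN and > 20 x ULN". Section 9 puts everything in one report: "The analyses described in this SAP will be included in the abbreviated Clinical Study Report except where otherwise noted". Section 6 states that there is no efficacy analysis and no power consideration.

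**The concern.** Two things catch the eye. First, a severity scale chosen by the lock date seems not to be fixed in advance, and the SAP was issued on 19-Oct-2019, after Revised Protocol 03 had unblinded the study. Second, the adverse event and laboratory tables both use the label CTC grade. If the two versions differ, a low neutrophil count could carry one grade as a reported event and another as a laboratory value, with no sign in the SAP that the scales are not the same. At stake would be the reader's ability to set the two kinds of table side by side. If the version rule also left the team a choice, the laboratory results could be open to influence.

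**Working it through.** The plan has no figure to reproduce on this point, since section 6 gives no power or error rate. The check is of the text, plus a count of the tables involved.

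**1. Do the rules contradict each other?** Section 7.1.1 governs adverse events and section 7.1.2 governs laboratory tests. An analyst knows which version applies to which data, and nothing must be reconciled before the tables can be run.

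**2. Are the laboratory tables sound in themselves?** Section 7.1.2 gives one rule for all laboratory tests and makes no exception for arm or visit. The same scale therefore grades every arm, and it grades both the baseline and the worst on-treatment value in each shift table. Between-arm comparisons and shifts are consistent whichever version is current at lock.

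**3. Does any analysis depend on the two scales agreeing?** In sections 7.6.2 to 7.6.10.4, as far as the text is visible, no table combines or cross-tabulates adverse event grades with laboratory grades. The two kinds of rate would not match even on one scale, for two reasons:

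- Section 7.6.10 limits each laboratory denominator to subjects who had the test, while the rest of section 7.6 uses all treated subjects.
- Section 5.1 counts adverse events from the first dose onwards, but laboratory evaluations only after it.

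**4. Is the version open to choice after the data are seen?** The rule is set in advance and points to a standard published outside the study. It allows no choice between versions. The same lock-date convention applies to MedDRA (7.1.1) and to the term lists for select adverse events, other events of special interest and immune-mediated events (7.1.1.1 to 7.1.1.3).

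**5. How many tables are involved?**

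- Analytes: 5 hematology + 5 chemistry + 5 electrolyte/glucose = 15.
- Gradings: 5 + 5 + (5 × 2 directions) = 20.
- Summaries: 20 × 2 (worst grade and shift) = 40 per cohort; 40 × 2 cohorts = 80.
- Also covered by tables in multiples of the upper limit of normal: ALT, AST and total bilirubin = 3. This leaves 15 − 3 = 12 analytes and 20 − 3 = 17 gradings.
- Adverse event summaries by grade: 2 (7.6.2) + 2 (7.6.3) + 2 (7.6.4) + 3 (7.6.5) + 2 (7.6.6.1) + 2 (7.6.7) = 13 per cohort.

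These figures show how far each rule reaches. They say nothing about how many subjects would change grade. To treat 40 or 80 as an upper bound on affected tables, one must suppose that every analyte's cut-offs differ between versions, and the SAP gives no support for that. The number is also partly arbitrary, because section 7.1.2 repeats the laboratory analyses in US units.

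**The case for a change.** The best case for the concern is one of consistency. Section 7.1.1 lets the coding dictionary float but ties the severity scale to the protocol, so the authors evidently saw a difference between the two; section 7.1.2 then floats a severity scale and gives no reason. For the floating term lists, the SAP promises to provide the terms in use at lock, but it makes no such promise for the laboratory version. For 12 of the 15 named analytes the graded tables are the only visible summary apart from listings. The study is unblinded, and one sentence plus a footnote would align the two rules.

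The observations are accurate. What stands is that the reader is helped if each graded table names its version. That is a matter of presentation, and section 9 leaves table layouts to the Data Presentation Plan, which is not at hand.

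The rest does not make a flaw. Unblinding matters little where the rule leaves no choice of version and treats all arms alike. There is also a practical reason for the asymmetry, though the SAP does not state it: a numeric laboratory result can be graded by program at any time, whereas an adverse event's grade is normally recorded during the study against the version then in force. Finally, aligning the rules has a price, because the main laboratory tables may become less comparable with other studies graded on a newer version.

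**Conclusion.** The concern does not hold. The SAP has two clear rules for two types of data, and following them gives sound descriptive laboratory tables. The effect on between-arm comparisons and on shifts from baseline is nil. The hepatic and thyroid tables in section 7.6.10.4 use limits of normal and do not depend on the version at all. A mismatch between adverse event and laboratory grades is possible but not shown: it is zero if the protocol's version is still the newest at lock, and otherwise it touches a comparison that the plan does not make. No error rate is at stake.

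This rests on three assumptions: that section 7.1.2 is applied uniformly to all arms and visits, as it reads; that no blacked-out text plans a joint analysis of the two kinds of grade; and that neither the protocol's CTCAE version nor the lock date is known here, so that a version difference can be neither confirmed nor excluded. The conclusion does not need the versions to match.

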7.4.2.5 Dose Omissions

For Cetuximab and Cisplatin omitted dose and the reason for the omission should be recorded in the site's source documentation.

7.4.3.1 Immune modulating medication

Not Applicable.

7.4.3.2 Subsequent Cancer Therapy

Not Applicable.

7.6 Safety

Analyses in this section will be tabulated for all treated subjects by treatment group “as treated”.

7.6.1 Deaths

Deaths will be summarized by treatment group:

- All deaths, reasons for death.
- Deaths within 30 days of last dose received, reasons for death.
- Deaths within 100 days of last dose received, reasons for death.

A by-subject listing of deaths will be provided for the all enrolled subjects population.

7.6.2 Serious Adverse Events

Serious adverse events will be summarized by treatment group:

- Overall summary of SAEs by worst CTC grade (any grade, grade 3-4, grade 5) presented by SOC/PT.
- Overall summary of drug-related SAEs by worst CTC grade (any grade, grade 3-4, grade 5) presented by SOC/PT.

All analyses will be conducted using the 30-day safety window.

A by-subject SAE listing will be provided for the “enrolled subjects” population.

7.6.3 Adverse Events Leading to Discontinuation of Study Therapy

AEs leading to discontinuation will be summarized by treatment group:

- Overall summary of AEs leading to discontinuation by worst CTC grade (any grade, grade 3-4, grade 5) presented by SOC/PT.
- Overall summary of drug-related AEs leading to discontinuation by worst CTC grade (any grade, grade 3-4, grade 5) presented by SOC/PT.

The analyses will be conducted using the 30-day safety window.

A by-subject AEs leading to discontinuation listing will be provided.

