2 STUDY DESCRIPTION

2.1 Study design

CA209-9TM was a randomized, double-blinded, placebo-controlled, phase 3 study of nivolumab or nivolumab plus cisplatin, in combination with radiotherapy in subjects with cisplatin ineligible and cisplatin eligible locally advanced squamous cell carcinoma of the head and neck (LAD SCCHN).

As of 15-Oct-2018, enrollment into the study was closed. At implementation of Revised Protocol 03, the study will be unblinded and placebo treatments will no longer be given. All enrolled subjects must be re-consented prior to continuing treatment on the study.

The study consists of two independent cohorts:

- **Cohort 1** will randomize subjects who are ineligible for cisplatin chemotherapy to receive nivolumab in combination with radiotherapy (**Arm A**) or cetuximab in combination with radiotherapy (**Arm B**).
- **Cohort 2** will randomize subjects who are eligible to receive cisplatin-based therapy to receive nivolumab in combination with cisplatin and radiotherapy (**Arm C**) or cisplatin and radiotherapy (**Arm D**).

In each cohort subjects will be randomized to the two treatment arms in a 1:1 ratio and stratified

by risk group (intermediate vs. high), PD-L1 tumor expression ($\geq 1\%$ vs. $< 1\%$ or indeterminate), and ECOG PS (0 vs. 1).

Cohort 1 (cisplatin ineligible):

[figure not shown]
- **Arm A** subjects will be administered Nivolumab in combination with intensity-modulated radiation therapy (IMRT).
 1. Nivolumab 240 mg single dose will be administered at w1d1 followed by 360 mg every 3 weeks for a total of 3 doses starting at w3d1 followed by 480 mg every 4 weeks for a total of 6 doses.
 2. IMRT 70 Gy will be administered as 35 fractions starting from w3d1 over 7 weeks.
- **Arm B** subjects will be administered cetuximab in combination with IMRT.
 1. cetuximab 400 mg/m² single dose will be administered at w2d1 followed by 250 mg/m² every week for a total of 7 doses starting at w3d1.
 2. IMRT 70 Gy will be administered as 35 fractions starting from w3d1 over 7 weeks.

Cohort 2 (cisplatin eligible):

- **Arm C** subjects will be administered Nivolumab in combination with Cisplatin and IMRT.
 1. Nivolumab 240 mg single dose will be administered at w1d1 followed by 360 mg every 3 weeks for a total of 3 doses starting at w3d1 followed by 480 mg every 4 weeks for a total of 6 doses.
 2. Cisplatin 100 mg/m² will be administered every 21 days starting at w3d1 for a total of 3 doses.

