are no records with indeterminant test result, then select those with unavailable result ('NOT EVALUABLE). If there are no records with unavailable test result, then select those with not reported or not available result (all other records). The latest record will be used as the baseline in the analyses. If there is more than one record for the latest date, then choose the one with the greatest specimen ID.

- Post baseline period:
 - On-treatment AEs will be defined as AEs with an onset date and time on or after the date and time of the first dose of study treatment (or with an onset date on or after the day of first dose of study treatment if time is not collected or is missing). For subjects who are off study treatment, AEs will be included if event occurred within a safety window of 30 days (or 100 days depending on the analysis) after the last dose of study treatment. No "subtracting rule" will be applied when an AE occurs both pre-treatment and post-treatment with the same preferred term and grade.
 - On-treatment evaluations (laboratory tests, pulse oximetry and vital signs) will be defined as evaluations taken after the day (and time, if collected and not missing) of first dose of study treatment. For subjects who are off study treatment, evaluations should be within a safety window of 30 days (or 100 days depending on the analysis) after the last dose of study treatment.
- For subjects who are off study treatment safety assessments will only be collected through 100 days post last dose.

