Unless otherwise specified, the AE summary tables will be restricted to on-treatment events regardless of the causality.

Analyses that take into account the multiple occurrences of a given adverse event will be conducted (see [Section 7.6.9](#)). To prepare these analyses, the CRF data will be processed according to standard BMS algorithms¹ in order to collapse adverse event records into unique records based on the preferred term. These data will be presented as the rate per 100 person-years of exposure. These analyses will take into account all on-treatment events (allowing more than 1 event per subject) and the total exposure time. The person-year exposure will be computed as the sum over the subjects’ exposure expressed in years where the exposure time is defined as

- (Date of last dose of study treatment - date of first dose of study treatment + 31 days (or 101 days, depending on the analysis))/365.25, for subject who are off study treatment and were followed for at least 30 days (or 100 days, depending on the analysis) after last dose of study treatment. Exposure time calculation will be based on all study therapy including administration of placebo drugs.
- (Last known alive date - date of first dose of study treatment +1)/365.25, for subjects who are still on-treatment or who are off study treatment and were followed less than 30 days (or 100 days depending on the analysis) after last dose of study treatment.

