Analyses in this section will be tabulated for all randomized subjects by treatment group as randomized, unless otherwise specified. Analyses will be performed separately for cisplatin ineligible and cisplatin eligible cohorts.

7.3.1 *Subject Disposition*

Number of subjects who discontinued study treatment along with corresponding reason will be tabulated by treatment group as treated. Reason for discontinuation will be derived from subject status CRF page. This analysis will be performed only on the all treated subjects population.

A by-subject listing for all treated subjects will be provided showing the subject's off treatment date and whether the subject continue in the treatment period/study along with the reason for going off treatment period/study.

7.3.2 *Demographics and Other Baseline Disease Characteristics*

The following demographic and baseline disease characteristics will be summarized and listed by treatment group as randomized:

- Age (continuous)
- Age categorization (< 65, ≥ 65 and < 75, ≥ 75 and < 85, ≥ 85, ≥ 75, ≥ 65)
- Sex (Male vs. Female)
- Race (White, Black or African American, Asian, Other)
- Asian race subgroups (Asian Indian, Chinese, Japanese, Korean, Taiwanese, Malay, Other Asian)
- Ethnicity (Hispanic/Latino and Not Hispanic/Latino) *

* Required for US subjects only

- Region (US/Canada, Europe, Asia, Rest of the World)
- ECOG PS (0 vs. 1 vs. >1)
- CNS metastasis at Baseline (Yes, No) - per radiographic tumour screening assessment
- Smoking Status (Current/Former, Never, Unknown)
- Smoking History (<= 20 pack year history vs. > 20 pack year history)
- PD-L1 (>=1%, <1%, indeterminate, non-evaluable)
- Creatinine clearance (< 60mL/min vs. >= 60mL/min)

Creatinine clearance is estimated by Cockcroft-Gault formula:

$$CCr = \{((140 \text{ age in years}) \times \text{weight in Kg}) / (72 \times \text{serum creatinine in mg/dL})\}$$

(for females, multiply the result by 0.85)

- Disease stage at initial diagnosis (stage III, IV)
- TNM Classification at initial diagnosis
- Time from Initial Disease Diagnosis to Randomization (< 1 year, 1 - < 2 year, 2 - < 3 year, 3 - < 4 year, 4 - < 5 year, ≥ 5 year).
- SCCHN risk of tumor recurrence (Intermediate vs High).
- Sites of diseases (all lesions) at baseline per Investigator
- Number of disease sites per subject (all lesions) at baseline per Investigator
- Number of target lesions, non-target lesions and disease sites at baseline per Investigator

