- Tumor burden: sum of the diameters of target lesions at baseline per Investigator

A listing of randomization scheme presenting randomized treatment group and as treated treatment group will be provided for all randomized subjects.

7.3.3 *Medical History*

Not Applicable.

7.3.4 *Prior Therapy Agents*

Prior systemic cancer therapy, prior radiotherapy, and prior surgery will be summarized by treatment group and overall and listed by subject.

7.3.5 *Physical Examinations*

Not Applicable.

7.3.6 *Baseline Physical Measurements*

Not Applicable.

7.4 *Extent of Exposure*

Analyses will be performed by treatment group “as treated”. Listings will include all available exposure data.

7.4.1 *Administration of Study Therapy*

A by-subject listing of study drug dosing will be provided.

7.4.2 *Modifications of Study Therapy*

No additional analysis will be provided.

7.4.2.1 *Dose Delays*

Each Nivolumab, Cetuximab, and Cisplatin infusion including corresponding placebo drugs may be delayed. A dose will be considered as actually delayed if the delay is exceeding 3 days (i.e. greater than or equal to 4 days from scheduled dosing date). Reason for dose delay will be retrieved from CRF dosing pages.

7.4.2.2 *Infusion Interruptions and Rate Changes*

Each Nivolumab, Cetuximab, and Cisplatin infusion including corresponding placebo drugs may be interrupted and/or the IV infusion rate can be reduced. This information will be retrieved from CRF dosing pages.

7.4.2.3 *Dose Escalations*

Dose escalations are not allowed for any of the study drug.

7.4.2.4 *Dose Reductions*

Nivolumab dose reductions are not allowed.

Cetuximab and Cisplatin dose may be reduced up to two times, need for further reduction will require drug discontinuation. Once a dose has been decreased, it should remain reduced for all

subsequent dosing unless dose is further reduced. Dose reduction information will be retrieved from CRF dosing pages.

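### The 30-day window in SAP section 7.6.3 drops AEs recorded as ending treatment when they begin on day 31 or later, which can happen when a 4-weekly nivolumab dose is late or on hold

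*SAP*

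**What the plan says.** AEs leading to discontinuation are a named safety endpoint (SAP section 4.1). Section 7.1.1 selects them by a CRF field: "Adverse events leading to study drug discontinuation are AEs with action taken regarding study drug(s"), the action being that the drug was discontinued. That sentence has no time limit.

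Three provisions then restrict the tables:
- Section 7.1.1 also says that, unless otherwise specified, "the AE summary tables will be restricted to on-treatment events regardless of the causality".
- Section 5.1 says what this means once a subject has gone off treatment for good: "AEs will be included if event occurred within a safety window of 30 days (or 100 days depending on the analysis"), counted from the last dose.
- Section 7.6.3 chooses the shorter window for the all-cause and drug-related discontinuation tables: "The analyses will be conducted using the 30-day safety window". It makes no exception.

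For Arms A and C, the last phase of nivolumab in section 2.1 is "followed by 480 mg every 4 weeks for a total of 6 doses". Section 7.4.2.1 allows late dosing: "Each Nivolumab, Cetuximab, and Cisplatin infusion including corresponding placebo drugs may be delayed". It also says when lateness counts: "A dose will be considered as actually delayed if the delay is exceeding 3 days".

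Safety assessments continue through 100 days after the last dose (section 5.1), and immune-mediated AEs are summarized with a 100-day window (section 7.6.7). Section 7.6.3 also provides a by-subject listing of AEs leading to discontinuation and states no window for it.

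**The concern.** A post-treatment window makes sense for general AE incidence, because it limits how many late, unrelated events are attributed to treatment. Here the investigator has already recorded that the AE ended dosing. A limit on time since last dose adds no specificity to that record. It can only remove events that meet the SAP's own definition.

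The limit also binds only on subjects who are off treatment, who are the subjects this endpoint is about. A subject who is held and then resumes is not off treatment during the hold, so the cut does not touch AEs in that interval.

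Efficacy analyses have been removed (section 6), so safety tables are the main content of the report. One possible result is an immune-mediated AE that starts on day 35 and ends nivolumab. It could appear in the section 7.6.7 table and be absent from the section 7.6.3 tables.

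**Working it through.** The SAP states no figure on this point, so there is nothing to reproduce. The check is day arithmetic, with the day of the last dose as day 0.

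**Inputs**
- Last day of the window: day 30. The exposure formula in section 7.1.1 (last dose minus first dose plus 31 days) counts both end days, so it runs to last dose + 30.
- Dosing interval I (section 2.1): 28 days for maintenance nivolumab, 21 for cisplatin and the earlier nivolumab doses, 7 for cetuximab.
- Lateness not counted as a delay (section 7.4.2.1): up to 3 days.
- Lateness D of the next dose: assumed, because the SAP gives no distribution.
- Section 5.1 speaks of when the event occurred; I read this as AE onset, as in its definition of on-treatment AEs.

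**Step 1: window against schedule**

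| Interval I | Latest day not counted as delayed (I + 3) | Days from there to day 30 | Lateness needed for onset on day 31 (31 − I) |
|---|---|---|---|
| 7 | 10 | 20 | 24 days |
| 21 | 24 | 6 | 10 days |
| 28 | 31 | −1 | 3 days |

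Only for 4-weekly dosing does the window close before the SAP's own limit for an undelayed dose, and then by one day.

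**Step 2: part of the dosing gap left uncovered**

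Uncovered days = max(0, I + D − 30). Share = uncovered days / (I + D).

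| D (days late) | I = 28 | I = 21 | I = 7 |
|---|---|---|---|
| 0 | 0/28 = 0% | 0% | 0% |
| 3 | 1/31 = 3% | 0% | 0% |
| 7 | 5/35 = 14% | 0% | 0% |
| 14 | 12/42 = 29% | 5/35 = 14% | 0% |
| 28 | 26/56 = 46% | 19/49 = 39% | 5/35 = 14% |

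These are shares of calendar days. They become shares of lost AEs only if onset is uniform over the gap, which is a further assumption.

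**Step 3: after the change**

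With no upper limit the uncovered days are 0. With the 100-day window they are max(0, I + D − 100). For I = 28 that is 0 for every D up to 72 days.

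**The case against.** **It is a uniform, openly stated convention.** Sections 7.6.2 to 7.6.5 all use 30 days, and section 7.1.1 announces the restriction to on-treatment events. This stands: the SAP does not contradict itself. But a window that suits AE incidence does not automatically suit an endpoint selected by action taken.

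**Nothing is lost from the report.** The by-subject listing in section 7.6.3 states no window and would probably show the case. The full AE listing and the 100-day immune-mediated table may show it too. This largely stands and limits the harm, but listings do not correct the tabulated counts.

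**The larger shares overstate the loss.** This stands. The cut depends on onset, not on the date of the decision to stop. An AE present at the day-28 visit that leads to a hold and later to stopping is kept. Only a new AE during a hold, or while a dose is late for another reason, is lost. Uniform onset over a long gap is therefore doubtful.

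**Direction.** A reader might infer that the rule flatters nivolumab throughout the trial. The SAP does not support that for the blinded period. Section 5.3 lists nivolumab-placebo as a study drug, section 7.1.1 includes placebo in the exposure time, and section 7.4.2.1 applies delays to placebo. A control subject's last dose could therefore have been placebo, on a schedule the available text does not show.

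**Disposition table.** A reader might also blame the window for any disagreement with section 7.3.1, where "Number of subjects who discontinued study treatment along with corresponding reason will be tabulated" without a time limit. The two can differ under any window. Section 7.3.1 uses the subject status page, while section 7.1.1 counts action on study drug(s), so stopping one drug of a combination may count without the subject leaving treatment.

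**Conclusion.** The point holds in a limited form. As written, both tables in section 7.6.3 exclude an AE recorded as ending treatment if it begins more than 30 days after the last dose, and nothing in the SAP exempts them.

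Nothing is lost when 4-weekly dosing stops on schedule at day 28. The loss needs a dose at least 3 days late. A dose exactly 3 days late, which the SAP does not count as delayed, exposes day 31 only, about 3% of the gap. The 14%, 29% and 46% figures are conditional on assumed delays of 7, 14 and 28 days, and are not estimates of undercounting. The true number cannot be worked out from the SAP and is probably small.

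After placebo removal the gap falls mainly on Arms A and C, because only they have 4-weekly dosing. Cisplatin and cetuximab need doses at least 10 and 24 days late. Before unblinding, no imbalance between arms can be shown. The tables are descriptive, so no test or power is affected. The change is worth making because the endpoint is named in section 4.1 and the data are already collected.

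**What to change.** In section 7.6.3, replace the window sentence with a rule on these lines: both tables include every AE with onset on or after first dose and a recorded action of drug discontinued, with no upper limit on time since last dose; a footnote gives, by arm, the number with onset more than 30 days after the last dose. Using the 100-day window already defined in section 5.1 would serve nearly as well.

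The same window in section 7.6.4 (dose delay or reduction) matters less, because a subject who resumes dosing is not off treatment when the AE occurs.

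The cost is one sentence and one programming filter, with no new data. The downsides are that these tables depart from the 30-day convention of the other AE tables, which the footnote makes visible, and that counts may rise slightly.
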